PROTOCOL TITLE: Evaluating Vitamin C in Septic Shock: A Randomized Double Blind Control
Trial

VERSION DATE: March 17, 2020

ABBREVIATIONS/DEFINITIONS

- BAL: Bronchoalveolar lavage
- BDAC: Biostatistical Design and Analysis Center
- DSMB: Data and Safety Monitoring Board
- ICU: intensive care unit
- LAR: legally authorized representative
- TA: Tracheal aspirate
- Vitamin C: also known as ascorbic acid

PROTOCOL TITLE: Evaluating Vitamin C in Septic Shock: A Randomized Double Blind Control Trial

VERSION DATE: March 17, 2020

STUDY SUMMARY

| | |
|---|---|
| Study Title | Evaluating Vitamin C in Septic Shock: A Randomized Double Blind Control Trial |
| Study Design | Phase 3, randomized double-blind |
| Primary Objective | Evaluate effect of Vitamin C supplementation on survival in patients presenting with septic shock |
| Secondary Objective(s) | Evaluate effect of Vitamin C supplementation on resolution of shock |
| Research Intervention(s)/ Investigational Agents | Vitamin C (ascorbic acid) |
| IND/IDE # (if applicable) | N/A: Exempt |
| Study Population | Patients admitted to ICU with septic shock |
| Sample Size (number of participants) | Approximately 140 Approximately 70 per group (study drug or placebo) |
| Study Duration for Individual Participants | Up to 4 days, plus a Day 28 chart review with no participant interaction |

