3.0 Study Endpoints/Events/Outcomes

3.1 Primary Endpoint/Event/Outcome:

First outcome endpoint for Specific Aim 1: all-cause mortality measured at ICU discharge.

Second outcome endpoint for Specific Aim 1: all-cause mortality measured at 28 days post Day 0.

3.2 Secondary Endpoint(s)/Event(s)/Outcome(s):

Outcome endpoint for Specific Aim 2: Difference in clinical outcomes between both groups at ICU discharge. Specific secondary endpoints may include, depending on power and final enrollment:

- a. Duration of vasopressor therapy post administration of Vitamin C (or placebo). Conclusion of vasopressor therapy will be defined as the time point when pressors are stopped, following which they are not restarted for 24 hours.
- b. Duration of ICU stay post administration of Vitamin C (or placebo).
- c. Time to lactate clearance post administration of Vitamin C (or placebo). Time of lactate clearance will be defined as the first time point at which measured lactate level drops below the normal level as defined by the measuring laboratory.
- d. Rate of lactate and procalcitonin clearance over 24, 48 and 96 hours following Vitamin C (or placebo) administration (in patients for whom values are available). Defined as the change in lactate and procalcitonin level from the initial measurement to the measurement at the designated time point if available, or closest measurement within 4 hours of the designated time point.
- e. Duration of mechanical ventilation post administration of Vitamin C (or placebo). Cessation of mechanical ventilation will be defined as the time of extubation following which re-intubation is not required for a full 24 hours.
- f. Incidence of need for renal replacement therapy during the 96 hour drug administration period
- g. Change in serum creatinine at 24, 48, 72, and 96 hours after Vitamin C (or placebo) administration compared to level at enrollment (in patients for whom values are available). The measurement closest in time to the designated time-point (within 12 hours) will be used. Patients who are dialysis-dependent at baseline or are currently receiving renal replacement therapy will be excluded from this endpoint.
- h. Change to SOFA and/or APACHE scores from initiation of Vitamin C (or placebo) as measured at 24, 48, 72, and 96 hours.

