- i. Total intravenous fluid administered from presentation until various intervals (3 hours, 6 hours, and 24hours), until resolution of shock, and from Vitamin C (or placebo) administration until resolution of shock.
- j. Effect of standard of care medications including corticosteroids as a sub-group analysis.

Outcome endpoint for Specific Aim 3: In general, clinical and biochemical characteristics associated with Vitamin C responsiveness will be examined. Specifics include:

- a. Assessment of whether time from onset of septic shock to receipt of Vitamin C (or placebo) influences effectiveness of Vitamin C therapy.
- b. Treatment effects as associated with or without initial presentation of inflammatory response

- Fever versus hypothermia
- Leukocytosis versus leukopenia
- Surgical versus medical source control
- c. Biobanking of blood specimens for future assessment of:
 - Vitamin C levels
 - Cytokine and chemokine levels
 - Danger associated molecular patterns (DAMPs)
 - Markers of necroptosis (RIP1 and RIP3)
 - Mitochondrial DNA and RNA for gene expressions
 - Genetic features favorable to Vitamin C therapy

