4.0 Study Intervention(s)/Investigational Agent(s)

4.1 Description:

This is a multi-center, randomized, double-blind, placebo-controlled clinical trial to compare Vitamin C versus placebo for patients presenting to the ICU with a diagnosis of septic shock.

The investigational product is parenteral Vitamin C (also known as ascorbic acid); 1000 mg bolus IV followed by a continuous infusion at 250 mg/hr or matched placebo.

4.2 Drug/Device Handling:

Investigational Drug Services and the research pharmacist will handle all drug requirements including randomization, blinding, and dispensing. Study clinicians as listed on the Delegation of Authority Log will manage ordering and prescribing. Clinical care staff will administer study drug/placebo infusions to the participant.

Vitamin C is available parenterally in a single dose 50 mL vial (500mg/mL). One 50 mL vial will be drawn up into five x 10 mL syringes containing 5000 mg of Vitamin C. These syringes will be refrigerated, protected from light, and given 9 day beyond use dating per USP 797 as a low-risk compounding product. The 5000mg/10mL pre-drawn syringes will be utilized in the preparation of the continuous infusion.

Total, Approximate Infusion Amounts

- 6875mg in first 24 hours, including initial bolus
- 6000mg per day for all following 24 hour periods
 - 7000mg maximum allowable per 24 hour period
- 25 grams per study period

Total infusion daily amount would be approximately 6000mg. More or less than 6000mg is acceptable given prioritization for septic shock treatment, body habitus concerns, or other clinically relevant decision made by the study clinician with the treating clinician. No more than 7000mg daily would be allowed, as a maximum amount of infusion. There will be no minimum amount provided as the infusion could be stopped early.

1. Preparation of Active Drug

- a. The Vitamin C infusion will be prepared as a 10mg/mL continuous infusion by adding the 5000mg (10 mL) syringe of Vitamin C to a 500 ml Normal Saline infusion bag.
- b. The Vitamin C 5000mg/500mL infusion bag will last 20 hours when running at the study rate of 250 mg/hour (25 ml/hour). The 1st infusion bag will last less than 20 hours since the initial bolus is administered from the infusion bag.
- c. The infusion bag will be given a 24 hour expiration date. At room temperature and protected from light, Vitamin C is compatible in Normal Saline for 24 hours.

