- d. The infusion will be protected from light with an amber bag. IV tubing will not be protected from light.

2. Preparation of Placebo

- a. The placebo infusion bag will be a 500 mL Normal Saline Infusion bag.
- b. The placebo infusion will be protected from light with a brown bag in the same manner as the active drug. IV tubing will not be protected from light.

3. Drug Administration

- a. The 1000mg bolus (100 ml) of active drug or placebo will be administered over 30 minutes from the active drug or placebo continuous infusion bag, respectively.
- b. After the initial bolus is complete, the continuous infusion will run at a rate of 250mg/hr (25 mL/hour).
- c. A dedicated line for the Ascorbic Acid or placebo infusions is not required. IV compatibility with other IV solutions should be checked per standard of practice.
- d. Infusion can be administered peripherally.
- e. Infusion will be stopped if the participant transitions to comfort care measures only

4.3 IND/IDE:

Not applicable, exempt. There is no intent to report to the FDA for a new indication, nor intent of this study is to support a significant change in the advertisement of Vitamin C. The administration of Vitamin C or placebo in septic shock population does not significantly increase risk or decrease acceptability of risk with its proposed route of administration and dosing.

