5.0 Procedures Involved

5.1 Study Design:

This is a multi-site, randomized, double-blind, placebo-controlled trial comparing a regimen of moderate-dose (6000 mg per day) Vitamin C supplementation versus placebo for the treatment of patients presenting to the ICU with septic shock. Both groups will continue to receive all other standard of care measures for septic shock as clinically indicated. Groups will be enrolled and receive study drug/placebo for 4 days (96 hours) or until 24 hours post-last pressor dose, whichever is sooner.

5.2 Study Procedures:

When a potentially eligible participant is identified, the PI or other clinical research team member will approach the individual with floor staff permission and coordination to explain the research.

PROTOCOL TITLE: Evaluating Vitamin C in Septic Shock: A Randomized Double Blind Control
Trial

VERSION DATE: March 17, 2020

After signing the consent and completing eligibility procedures, IDS will be notified. IDS will perform randomization and dispense appropriate study drug/placebo infusion materials.

Infusions must be started within 24 hours post-presentation of septic shock. Those participants who consent but cannot start an infusion within 24 hours will still follow all research procedures related to data collection except for banking of biospecimens.

Participants randomized to Vitamin C will receive IV parenteral Vitamin C; with a 1000 mg bolus to start and followed by a continuous infusion at 250 mg/hr for four days or off pressors for 24 hours, whichever is sooner. Placebo will be given as a matched infusion on the same schedule.

Chart review will take place at 24 hour time periods (Day 0, 1, 2, 3, and 4).

Blood draws for biobanking will occur at Day 0, 1, and 3 (0, 24 and 72 hours), 25 mL on day 0, and then 20 mL on days 1 and 3. Patients discharged from the hospital will not undergo blood draws following discharge. Those still in the hospital, any floor or unit, will have blood drawn if clinically possible. Blood draw will be based on a convenience sample only. Blood draw will only be done when study clinician is available and when time is available for processing and transporting. Not all participants will have all, or any, blood draw done for biobanking.

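### Secondary item i has no IV-fluid total that both starts at study drug and ends at a fixed time; the two totals that run to resolution of shock largely restate time in shock

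*Combined protocol and SAP*

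**What the plan says.** Item i of Section 3.2 contains five fluid totals. Four start at presentation: "Total intravenous fluid administered from presentation until various intervals (3 hours, 6 hours, and 24hours), until resolution of shock". The fifth starts at study drug. So three have a fixed end and two end when shock resolves: "until resolution of shock, and from Vitamin C (or placebo) administration until resolution of shock".

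Resolution of shock is itself something the trial sets out to change. The Study Summary gives the secondary objective as "Evaluate effect of Vitamin C supplementation on resolution of shock". The term is not defined. The nearest definition is in item a: "Conclusion of vasopressor therapy will be defined as the time point when pressors are stopped, following which they are not restarted for 24 hours". Item i does not refer to it.

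Section 4.2 gives both arms a study infusion with volume: "The 1000mg bolus (100 ml) of active drug or placebo will be administered over 30 minutes", then 25 mL/h. Section 5.1 continues it for 96 hours "or until 24 hours post-last pressor dose, whichever is sooner". Item i does not say whether this volume counts as IV fluid.

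Section 5.2 allows the infusion to start up to 24 hours after presentation. Section 16.1 compares continuous outcomes by two-sample t test, with linear regression for covariate adjustment. It gives no scaling by time and no rule for participants who die or never resolve.

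**The concern.** A total over a window that ends at a participant's own recovery is roughly the fluid rate multiplied by the time in shock. If one arm recovers sooner, its total falls even when clinicians give exactly as much fluid per hour. The comparison then repeats item a (vasopressor duration) in millilitres and could be reported as an independent fluid-sparing effect.

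Death raises a second problem. A participant who dies in shock never reaches the end of the window. If the window is cut at death, an early death produces one of the lowest totals and looks favourable.

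The fixed windows do not fill the gap. An infusion started at hour 20 leaves 4 hours of the 24-hour total after treatment; one started at hour 24 leaves none. The 3- and 6-hour totals are wholly pre-treatment for anyone who starts after hour 6. Item i therefore offers no clean comparison of fluid given after treatment.

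**Working it through.** **Inputs from the protocol (Sections 4.2 and 5.1).** Bolus of 100 mL over 0.5 h, then 25 mL/h, at 10 mg/mL, capped at 96 h.

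**Step 1: reproduce the protocol's own amounts.** Study volume by t hours after start is V(t) = 100 + 25 × (t − 0.5) for 0.5 ≤ t ≤ 96, and constant after that.
- V(24) = 100 + 25 × 23.5 = 687.5 mL, or 6,875 mg. This equals the stated first-day amount.
- V(96) = 100 + 25 × 95.5 = 2,487.5 mL, or 24,875 mg. This agrees with the stated 25 g.

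**Step 2: study infusion inside the window from study drug to resolution.** This assumes that study fluid counts, that resolution coincides with the end of vasopressors, and that the infusion is not stopped early.

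| Shock resolves at | Study infusion in window |
|---|---|
| 12 h | 387.5 mL |
| 24 h | 687.5 mL |
| 48 h | 1,287.5 mL |
| 72 h | 1,887.5 mL |
| 96 h or later | 2,487.5 mL |

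A 24 h difference within the cap is 25 × 24 = 600 mL. Beyond 96 h it is nil: 100 h against 130 h gives 0 mL.

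**Step 3: all fluid, with identical hourly need.** The documents give neither times in shock nor other fluid rates, so these are assumptions: exponential time in shock with mean m of 40 or 30 h, and a constant non-study rate r of 50 or 100 mL/h in both arms.

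Mean study infusion = 25 × m(1 − e^(−96/m)) + 175 × m(1 − e^(−0.5/m)). This gives 996 mL for m = 40 and 806 mL for m = 30, a gap of 190 mL. Mean non-study fluid is r × m.

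| r | Mean 40 h | Mean 30 h | Gap | Share from study infusion |
|---|---|---|---|---|
| 50 mL/h | 996 + 2,000 = 2,996 mL | 806 + 1,500 = 2,306 mL | 690 mL (23%) | 190/690 = 28% |
| 100 mL/h | 996 + 4,000 = 4,996 mL | 806 + 3,000 = 3,806 mL | 1,190 mL (24%) | 190/1,190 = 16% |

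Excluding study fluid leaves 2,000 against 1,500 mL, or 4,000 against 3,000 mL, still 25% lower. The window has to change as well as the count.

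**Step 4: early death, window cut at death.** Assumptions: the same exponential mean of 40 h and the same fluid rate in both arms; deaths spread evenly over the first 24 h in 10% of one arm and 30% of the other; non-study fluid only. Mean window for those who die is 40 − (40²/24)(1 − e^(−24/40)) = 9.9 h. The arm means are 0.9 × 40 + 0.1 × 9.9 = 37.0 h and 0.7 × 40 + 0.3 × 9.9 = 31.0 h. The arm with more deaths records about 16% less fluid.

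**Step 5: fixed window from first infusion.** Over 24 h the scheduled study infusion is 687.5 mL in each arm, so its built-in difference is 0 mL while infusions run to schedule.

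**The case against.** The strongest reply is that fluid given until shock resolves is a legitimate quantity. Section 2.2 describes the burn-study finding as less fluid needed to reach a haemodynamic goal, which is a cumulative volume and not an hourly rate. If Vitamin C ends shock sooner and patients receive less fluid, that is a real consequence of treatment. This stands. A reader might infer that the totals to resolution are invalid or must be deleted; the documents do not support that. They answer a different question, one driven by duration, and overlap with item a makes them correlated with it, not wrong.

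A reader might also infer that the study infusion by itself explains an apparent fluid-sparing effect. It does not: it supplies 16 to 28% of the gap in the illustration, stops at 96 hours, and may be stopped earlier. Nor do the documents say that study fluid is counted; they are silent.

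The constant hourly rate in the illustration is a simplification. It suits the total from presentation least, because eligibility requires at least 30 mL/kg of prior fluid resuscitation and part of that total is therefore front-loaded.

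Finally, Section 3.2 says these endpoints may be included depending on power and enrolment. The stakes are limited accordingly.

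**Conclusion.** The point holds in a limited form. Item i lacks a fluid total anchored at study drug with a fixed end, and the two totals to resolution largely restate time in shock. A lower total there is real as a volume but is not evidence of lower fluid need per unit time.

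From the protocol's own rates, the infusion component is 600 mL per 24 h of difference in resolution time within the 96 h cap, if study fluid counts. The overall gap of 23 to 24% and the 16% effect of early deaths rest on the assumptions stated with them. With equal resolution times and equal early deaths, no distortion arises. Nothing here affects the mortality comparison. This is a worthwhile correction to an optional secondary endpoint.

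**What to change.** Reword item i as follows.

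1. Make the main fluid comparison non-study IV fluid over 24, 48 and 96 hours from first infusion, which are time points already used in items d, g and h. Exclude study-drug and placebo volume.
2. State a rule for deaths within the window, because a fixed window is also cut short by death. Options are to rank deaths as the worst outcome, or to report fluid per hour alive alongside mortality.
3. If a total to resolution is kept, define resolution of shock, say how participants who never resolve are handled, label the total descriptive, and present it next to item a.

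The cost is a change of wording and a little more analysis. Fluid volumes must also be abstracted through 96 hours even after shock resolves. Section 5.2 provides chart review on Days 0 to 4 but does not list fluid volume among the data collected, so the sponsor should confirm that it is recorded.

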4.0 Study Intervention(s)/Investigational Agent(s)

4.1 Description:

This is a multi-center, randomized, double-blind, placebo-controlled clinical trial to compare Vitamin C versus placebo for patients presenting to the ICU with a diagnosis of septic shock.

The investigational product is parenteral Vitamin C (also known as ascorbic acid); 1000 mg bolus IV followed by a continuous infusion at 250 mg/hr or matched placebo.

4.2 Drug/Device Handling:

Investigational Drug Services and the research pharmacist will handle all drug requirements including randomization, blinding, and dispensing. Study clinicians as listed on the Delegation of Authority Log will manage ordering and prescribing. Clinical care staff will administer study drug/placebo infusions to the participant.

Vitamin C is available parenterally in a single dose 50 mL vial (500mg/mL). One 50 mL vial will be drawn up into five x 10 mL syringes containing 5000 mg of Vitamin C. These syringes will be refrigerated, protected from light, and given 9 day beyond use dating per USP 797 as a low-risk compounding product. The 5000mg/10mL pre-drawn syringes will be utilized in the preparation of the continuous infusion.

Total, Approximate Infusion Amounts

- 6875mg in first 24 hours, including initial bolus
- 6000mg per day for all following 24 hour periods
 - 7000mg maximum allowable per 24 hour period
- 25 grams per study period

Total infusion daily amount would be approximately 6000mg. More or less than 6000mg is acceptable given prioritization for septic shock treatment, body habitus concerns, or other clinically relevant decision made by the study clinician with the treating clinician. No more than 7000mg daily would be allowed, as a maximum amount of infusion. There will be no minimum amount provided as the infusion could be stopped early.

1. Preparation of Active Drug

- a. The Vitamin C infusion will be prepared as a 10mg/mL continuous infusion by adding the 5000mg (10 mL) syringe of Vitamin C to a 500 ml Normal Saline infusion bag.
- b. The Vitamin C 5000mg/500mL infusion bag will last 20 hours when running at the study rate of 250 mg/hour (25 ml/hour). The 1st infusion bag will last less than 20 hours since the initial bolus is administered from the infusion bag.
- c. The infusion bag will be given a 24 hour expiration date. At room temperature and protected from light, Vitamin C is compatible in Normal Saline for 24 hours.
- d. The infusion will be protected from light with an amber bag. IV tubing will not be protected from light.

2. Preparation of Placebo

- a. The placebo infusion bag will be a 500 mL Normal Saline Infusion bag.
- b. The placebo infusion will be protected from light with a brown bag in the same manner as the active drug. IV tubing will not be protected from light.

3. Drug Administration

- a. The 1000mg bolus (100 ml) of active drug or placebo will be administered over 30 minutes from the active drug or placebo continuous infusion bag, respectively.
- b. After the initial bolus is complete, the continuous infusion will run at a rate of 250mg/hr (25 mL/hour).
- c. A dedicated line for the Ascorbic Acid or placebo infusions is not required. IV compatibility with other IV solutions should be checked per standard of practice.
- d. Infusion can be administered peripherally.
- e. Infusion will be stopped if the participant transitions to comfort care measures only

4.3 IND/IDE:

Not applicable, exempt. There is no intent to report to the FDA for a new indication, nor intent of this study is to support a significant change in the advertisement of Vitamin C. The administration of Vitamin C or placebo in septic shock population does not significantly increase risk or decrease acceptability of risk with its proposed route of administration and dosing.

5.0 Procedures Involved

5.1 Study Design:

This is a multi-site, randomized, double-blind, placebo-controlled trial comparing a regimen of moderate-dose (6000 mg per day) Vitamin C supplementation versus placebo for the treatment of patients presenting to the ICU with septic shock. Both groups will continue to receive all other standard of care measures for septic shock as clinically indicated. Groups will be enrolled and receive study drug/placebo for 4 days (96 hours) or until 24 hours post-last pressor dose, whichever is sooner.

5.2 Study Procedures:

When a potentially eligible participant is identified, the PI or other clinical research team member will approach the individual with floor staff permission and coordination to explain the research.

PROTOCOL TITLE: Evaluating Vitamin C in Septic Shock: A Randomized Double Blind Control
Trial

VERSION DATE: March 17, 2020

After signing the consent and completing eligibility procedures, IDS will be notified. IDS will perform randomization and dispense appropriate study drug/placebo infusion materials.

Infusions must be started within 24 hours post-presentation of septic shock. Those participants who consent but cannot start an infusion within 24 hours will still follow all research procedures related to data collection except for banking of biospecimens.

Participants randomized to Vitamin C will receive IV parenteral Vitamin C; with a 1000 mg bolus to start and followed by a continuous infusion at 250 mg/hr for four days or off pressors for 24 hours, whichever is sooner. Placebo will be given as a matched infusion on the same schedule.

Chart review will take place at 24 hour time periods (Day 0, 1, 2, 3, and 4).

Blood draws for biobanking will occur at Day 0, 1, and 3 (0, 24 and 72 hours), 25 mL on day 0, and then 20 mL on days 1 and 3. Patients discharged from the hospital will not undergo blood draws following discharge. Those still in the hospital, any floor or unit, will have blood drawn if clinically possible. Blood draw will be based on a convenience sample only. Blood draw will only be done when study clinician is available and when time is available for processing and transporting. Not all participants will have all, or any, blood draw done for biobanking.

